5.1 Duration of Study

Patients enrolled in this study will participate for approximately 12 weeks. The participants will be consented at the end of their cancer treatment. The participant will remain on study until their next clinic visit (~3 months).

There will be up to three in-person interactions with the patients in this study: during a clinic visit where the study is introduced, on the day of the baseline visit, and at the time of their 3-month follow up or post-intervention visit. Patients will be approached by the study coordinator for participation in this study during routine clinic visits. If a provider identifies eligible patients in advance of their scheduled visit and notifies the study coordinator, the study coordinator will contact the patient via telephone prior to their clinic visit to introduce the study and assess interest. If the patient is interested, the study coordinator will obtain a telephone consent. At the next scheduled visit, the study coordinator will obtain the patient's signed consent and provide a physical hardcopy of their signed consent form to the patient prior to initiating any study activities.

There will also be three phone calls from the study team: prior to the baseline visit to remind the patient to fast for blood collection, at the end of week 1 to ensure successful use of the fitness tracker, and prior to the post-intervention visit to remind the patient to fast again. For all subjects, study staff plans to send out email reminders so they can sync their Fitbits in time and log into UNC CHART to ensure data quality.

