After the above measurements and vitals are taken, patients will complete an enrollment survey including the GPAQ survey to measure baseline activity and baseline FACT-G assessment (27, 28). Pre-intervention FACT-G total score and sub-scale scores (physical well-being, social well-being, emotional well-being and functional well-being) will be compared to post-intervention scores. Finally, baseline fasting glucose, insulin and LDL will be obtained at the time of study baseline activities. Blood and urine will be collected and stored for potential future metabolomic profiling. Patients will then be randomized to either receive or not receive tailored feedback messages through UNC CHART. Participants randomized to the message arm will begin receiving encouragement and reminder UNC CHART messages to increase physical activity weekly based on the CHART algorithm (Appendix 1). Participants on the feedback arm will receive 1 message per week during the 3-month study period.

For the first week after initiating the study, each patient's baseline step count will be obtained from the fitness tracker. The mean step count over these 7 days will represent the patient's baseline step count. After the baseline week is completed, the study team will contact patients to ensure successful use of technology.

At the time of next follow up visit, the patient will undergo repeat weight, height, waist circumference, and hip circumference assessment. Heart rate and blood pressure will also be recorded at the follow up visit. The patient will complete a post-intervention acceptability survey and complete a post-intervention FACT-G assessment. Post-intervention fasting glucose, insulin, and LDL will be performed. Urine and blood will also be banked via the Tissue Procurement Facility (TPF) at the Lineberger Comprehensive Cancer Center (LCCC) for future metabolomic profiling.

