5.4 Removal of Patients from Protocol

Patients will be removed from the protocol if musculoskeletal injury is incurred. Patient will also be removed from the protocol at patient request. The patients will receive a phone call following week 1 to assess for adverse events, but will not be contacted in weeks 2-12 to minimize bias from the Hawthorne effect of repetitive phone calls while on trial. Patients will be instructed to contact study personnel if any concern for injury or adverse event related to trial enrollment and be removed from study.

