8.0 STATISTICAL CONSIDERATIONS

8.1 Study Design

This is a randomized, single-center, tailored feedback message intervention trial. The project will use fitness trackers to measure increase in physical activity from baseline in women randomized to receive weekly motivational feedback messages. A control group will receive a fitness tracker but no feedback message reinforcement. The primary objective of the study is to detect a 2,000 mean daily step increase from baseline in patients undergoing the feedback message intervention. Therefore, patients will be randomized, 1:1 using a 6-block scheme.

Exploratory objectives include gathering data on the acceptability of the intervention, as well as desired frequency, timing, and content of messages for use in a larger trial. Additionally, outcomes that will be the goal of a larger trial will be explored. These endpoints include: BMI, waist/hip ratio, QOL as measured by FACT-G, and serum metabolic markers (fasting insulin, glucose, and LDL).

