8.2 Sample Size and Accrual

Prior studies and systematic reviews have shown participant standard deviations in daily steps of approximately 1300-1800 steps/day (20, 30, 32). Furthermore, previous studies measuring the impact of similar interventions on patient fitness levels have observed a patient step count change score standard deviation of approximately 1700 steps/day (29), where change score is defined as the change in step count from baseline to a particular week post-baseline. To determine whether there is a significant increase in physical activity among patients receiving the feedback messaging intervention versus those that do not receive the intervention, we will compare participant change scores between the each arm in our study. Assuming a participant change score standard deviation of 1800 steps/day, we estimate that 15 women will provide 80% power to detect a 2000-step difference in change score between arms (30), utilizing a two-sided Wilcoxon Two-Sample test with an alpha of 0.05. Within each arm, we will have sufficient power with $n = 15$ subjects to determine whether change scores within an arm are significantly different from zero, and we estimate that we will have >95% power to detect a change score of at least 2000 steps/day using a two-sided Wilcoxon Signed Rank test, assuming an alpha of 0.05 and a patient change score standard deviation of 1800 steps/day. We will also perform similar tests utilizing change scores computed at 4 weeks and 8 weeks post-baseline to determine whether these effects appear earlier on during the intervention period. We will also directly examine linear trends in daily step count with respect to time in days, as well as the overall three month average change in step count from baseline, via linear mixed models. Prior similar fitness intervention noted a 5% attrition rate in a large trial over 6 months time (29). To make a conservative estimate we will allow for 20% attrition and thus aim to enroll 39 total patients to obtain 36 evaluable datasets (18 patients in each arm). All power calculations were computing using G*Power software version 3.1.9.2 (33).

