8.3 Data Analysis Plans

Our primary objective will be measured by comparing patients baseline step counts (defined as the mean step count recorded by the fitness tracker for each participant in the first 7 days following enrollment) to week 12 (final week of study participation) step counts. The week 12 step counts will also be the mean step count recorded by the fitness tracker over 7 days in a participant's final week on the study. The

mean change in steps in the intervention group will be compared to the no-intervention group using a Wilcoxon Two-sample test.

For our exploratory objectives:

Acceptability of the intervention will be measured, as previously reported, using the results of a post-intervention Likert scale survey (29). At study conclusion, patients randomized to the feedback messaging arm will complete a post-intervention survey regarding the acceptability of the invention. Question #1 of the post-intervention survey will ask patients about the acceptability of the intervention using a 5-point Likert scale. The completion survey will also include information about desired frequency of messages, desired content of messages, and timing of messages. The information obtained in this portion of the study will allow improvements to be made in our intervention prior to implementation of a larger randomized trial. The acceptability of the intervention will be defined as the proportion of patients answering favorably (very helpful or somewhat helpful) to question #1 on the completion survey. We aim to have 80% acceptability. Previous surveys of adults have shown 81% to find mobile health interventions acceptable (34). We will report the proportion of subjects reporting favorable responses to question #1 on the completion survey and the corresponding 95% CI.

Finally, we will look for decrease in BMI, improved W/H ratio, improved QOL, and improved serum metabolic markers. These data will be preliminarily evaluated in this pilot study, but will represent the primary endpoints of interest in the randomized trial to be conducted following completion of this pilot. Basic descriptive and comparative statistics will be performed to evaluate BMI, QOL, W/H ratio and insulin/glucose/LDL levels as exploratory endpoints at each time point, in addition to the change in each exploratory endpoint between time points. All computed descriptive statistics would be stratified by study arm.

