11.0 APPENDICES

Appendix 1: UNC CHART Feedback Message Library

PROJECT: MOVES
SUBJECT: FEEDBACK INFORMATION

Data input

- Data will be input into the feedback systems in two ways from FitBIT through Validic
- One physical activity variable will be used for feedback for each participant.
 - Steps per day
 - Used to compute: Average steps per day (average over days provided for that week)
- Data structure
 - The raw data will include steps and MVPA minutes for each day of the week.
 - Each weekly report will be updated based on the data retrieved for the previous 7 days.
 - Example: data below would be used to create report opened to participant on Monday MAR 14th.
 - Data will be used to compute weekly summary variables that will be used to control the CHART feedback.

Daily data for 1 participant over first 2 weeks of intervention

PID	Date	Day of week	Steps	NOTE
1562	3/07/2016	MON	0	Sync, but no Wear Steps < 2000, not used
1562	3/08/2016	TUE	6000	OK
1562	3/09/2016	WED	6000	OK
1562	3/10/2016	THU	8000	OK
1562	3/11/2016	FRI	4000	OK
1562	3/12/2016	SAT	.	No Sync, not 0
1562	3/13/2016	SUN	.	No Sync, not 0
1562	3/14/2016	MON	5000	OK

1562	3/15/2016	TUE	7000	OK
1562	3/16/2016	WED	8000	OK
1562	3/17/2016	THU	1000	Sync, but no wear steps <2000, not used
1562	3/18/2016	FRI	9000	OK
1562	3/19/2016	SAT	4000	OK
1562	3/20/2016	SUN	6000	OK

Weekly summary variables computed from daily data.

intWEEK	WKStartdate	nDaysMonitor	nDaysSync	StepPERday	goalSTEP	NOTmeetSTEP	NEWgoalstep
1	3/07/16	4	5	6000	5000	0	6500
2	3/14/16	6	7	6500	6500	0	7000

Computed Variables and Criteria

Weekly summary variables computed from daily data.

intWEEK	WKStartdate	nDaysMonitor	nDaysSync	StepPERday	goalSTEP	NOTmeetSTEP	NEWgoalstep
1	3/07/16	4	5	6000	5000	0	6500
2	3/14/16	6	7	6500	6500	0	7000

Variables for Feedback

Variable name	Limit	Compute	Description
intWEEK	1 to 6		Week of intervention
nDayMonitor	0 to 7	number of days with more than 2000 steps	Number of Days monitored
nDaySync	0 to 7	FITBIT only: number of non-missing days	Number of Days synced
StepPERday	Only computed if: nDAYsmonitored > 2	Average steps for days with more than 2000 steps	STEPS per Day
goalSTEP	5000 to 12000	Based on previous weeks step average and goal achievement.	Weekly Goal for Steps Step Goal for Current intervention WEEK

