2	IF nDaymonitor < 3	-	-	Not enough days monitored	
You did not wear, or sync, your Fitbit enough last week to give you a personal goal and meaningful feedback.
 
Please be sure to wear your Fitbit each day, keep it charged, and sync using the app or your home computer.

2	IF nDaymonitor >= 3	(STEPperday/goalSTEP) >= 0.90		Wore monitor Meeting Goal	Congratulations on your success last week! Every little move you make helps to strengthen your heart and gives you more energy. Getting healthy after a diagnosis of endometrial cancer is so important. What did you do last week that helped you fit more steps into your day? Use what you learned last week to help you meet your goal next week.
2	IF nDaymonitor >= 3	(STEPperday/goalSTEP) < 0.90	NOTmeetSTEP <= 2	Wore monitor NOT meeting goal NOT stuck	Some weeks it can be hard to fit in all of the activity that you'd like. Plan out your week in advance to find time to be active. Mark your calendar and stick with it. On very busy days, a few brisk 10-minute walks, can really help refresh and de-stress. Focusing on your health after your cancer diagnosis is so important.
3	IF nDaymonitor < 3			Not enough days monitored	
You did not wear, or sync, your Fitbit enough last week to give you a personal goal and meaningful feedback.
 
Please be sure to wear your Fitbit each day, keep it charged, and sync using the app or your home computer.

3	IF nDaymonitor >= 3	(STEPperday/goalSTEP) >= 0.90	NA	Wore monitor Meeting Goal	Great job! You are making excellent progress toward 10,000 steps and a healthier life! Find an exercise buddy to make your physical activity more fun. Ask a coworker, friend, or family member to go for a walk or bike ride with you. See if you can make it a weekly date.
3	IF nDaymonitor >= 3	(STEPperday/goalSTEP) < 0.90	NOTmeetSTEP <= 2	Wore monitor NOT meeting goal NOT stuck	Having an exercise buddy can help you meet your steps goal. Ask a coworker, friend, or family member to go for a walk with you. Exercise is more fun with a buddy, and you will be less likely to skip if you know someone's counting on you.
3	IF nDaymonitor >= 3	(STEPperday/goalSTEP) < 0.90	NOTmeetSTEP > 2	Wore monitor NOT meeting goal Stuck	Think about what has been getting in the way of your walking. What can you do to get moving in the right direction? If time is an issue, think about how you can fit three, 10-minute walks into your day. Every step you take will add up to a healthier, happier you!

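### Only the feedback arm is told to wear and charge the tracker that measures the primary endpoint; the effect cannot be sized from the documents, and levelling the prompt is cheap

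*Combined protocol and SAP*

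**What the plan says.** In Appendix 1, the My NEW Goals section of the weekly CHART report has a row for women with fewer than 3 monitored days. In most weeks that row ends: "Please be sure to wear your Fitbit each day, keep it charged, and sync using the app or your home computer". Footnote 1 of the Section 6.1 table limits the weekly messages to the feedback arm in weeks 2–12. Section 8.1 says of the others: "A control group will receive a fitness tracker but no feedback message reinforcement".

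Support common to both arms is tracker and CHART training at the baseline visit, one call, and emails. On the call, Section 5.2 says: "After the baseline week is completed, the study team will contact patients to ensure successful use of technology". On the emails, Section 5.1 says: "For all subjects, study staff plans to send out email reminders so they can sync their Fitbits in time and log into UNC CHART", with data quality as the stated purpose. Section 5.4 adds that patients "will not be contacted in weeks 2-12 to minimize bias from the Hawthorne effect of repetitive phone calls while on trial".

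The tracker is also the measuring instrument. The baseline value is its mean over the first 7 days, and Section 8.3 continues: "The week 12 step counts will also be the mean step count recorded by the fitness tracker over 7 days". No rule for unworn or unsynced days is given there. A rule exists only in the message algorithm of Appendix 1, where the weekly figure is described as "Average steps for days with more than 2000 steps".

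**The concern.** Help with collecting the outcome should be the same in both arms, so that a difference in the recorded endpoint can be read as a difference in behaviour. Here a feedback woman who has largely stopped wearing the device is told so and, in most weeks, asked to wear and charge it. A control with the same record gets nothing described as a wear or charge prompt. By the Section 6.1 table the messages start after the baseline week, so the imbalance falls on follow-up only and enters the change score directly.

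Two things are at stake. Recorded steps depend on wear as well as walking, so part of an arm difference could be measurement. The set of women with usable data at weeks 4, 8 and 12 could also be selected differently by arm, in a trial that enrols 39 to obtain 36 evaluable datasets. Section 1.2 makes the worry reasonable: it reports that earlier CHART wearables studies improved self-monitoring compliance while activity changed only modestly.

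**Working it through.** **1. Support for tracker use after baseline, by arm**

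| Support | Feedback | Control | Source |
|---|---|---|---|
| Call at end of week 1 | yes | yes | 5.1, 5.2 |
| Email: sync and log in | yes | yes | 5.1 |
| Told that wear or sync was insufficient | yes, below 3 monitored days | none described | App. 1, 6.1 |
| Told to wear, charge and sync | yes, below 3 monitored days, 7 of 11 rows | none described | App. 1, 6.1 |

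The remaining call, before the post-intervention visit, is a fasting reminder for both arms.

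**2. When the prompt is present.** The wear/charge/sync sentence is in the rows for weeks 1, 2, 3, 4, 6, 7 and 9. Rows 5, 8 and 10 say only that wear or sync was insufficient. Row 11 of that section is a congratulation with no wear wording. So 3 of the last 4 rows (8, 10, 11) lack the sentence. The progress panel of the same report also mentions insufficient wear or sync, but is specified for weeks 1–6. Eleven rows match eleven message weeks (2–12), and each report uses the previous 7 days. On that reading, row 9 opens in study week 10 and row 11 in week 12, the endpoint week. The asymmetry is weakest where the primary endpoint is measured.

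**3. The plan's own scale.** Section 8.2 states: "Assuming a participant change score standard deviation of 1800 steps/day, we estimate that 15 women will provide 80% power", for a 2,000-step difference. Reading 15 as per arm:
- standardised effect 2000/1800 = 1.111
- effective n for the Wilcoxon test 15 × 3/π = 14.32
- noncentrality 1.111 × √(14.32/2) = 2.97
- power 81.7% (80.4% by simulation)

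The stated 80% reproduces, so 2,000 steps with SD 1,800 is a sound yardstick.

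**4. Can the size be derived?** Suppose a share p of women fall below 3 monitored days, and a prompted feedback woman then wears the device d more days in the endpoint week than a similar control, at S steps/day. If unworn days count as zero, the spurious shift in arm means is p × d × S/7. None of p, d and S is in the documents. Assumed: p = 10–20%; d = 1–5 (5 being a move from two worn days to seven); S = 4,000–8,000.
- Low end: 0.10 × 1 × 4000/7 = 57 steps/day, 3% of 2,000.
- High end: 0.20 × 5 × 8000/7 = 1,143 steps/day, 57% of 2,000.
- If unworn days are dropped, the shift by this route is 0.

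The Appendix 1 example shows how much the scoring rule matters. Its first week totals 24,000 steps, which gives 24000/4 = 6,000 over days above 2,000 steps, 24000/5 = 4,800 over synced days, and 24000/7 = 3,429 over all seven. A range from nothing to more than half the target is not an estimate.

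**5. Can the direction be derived?** If unworn days count as zero, better wear in the feedback arm favours feedback. If poorly engaged women are retained by prompts in the feedback arm while similar controls become non-evaluable, the remaining controls are the more motivated ones, which works against feedback. The documents do not allow these to be netted.

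**The case against.** The strongest reply is that wear prompts belong to the package under test: Section 1.2 names self-monitoring as an advantage of trackers, and the control condition is defined as no messages. That is a legitimate design view. But the primary objective in Section 2.1 is physical activity, not tracker use, and Section 5.1 already gives sync reminders to everyone for data quality. Extending these to wear and charging leaves goals, progress and encouragement as the contrast.

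Other points stand and limit the concern. The prompt fires only below 3 monitored days. Section 5.3.4 says women must log on to CHART to see messages, so a disengaged woman may miss it. The email text itself is not in the documents, so the absence of wear wording is read from a one-sentence description.

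A reader might infer 5–10% longer wear across the whole feedback arm, hence 6000 × 5% = 300 to 6000 × 10% = 600 steps/day, or 15–30% of the target. The documents do not support this. The prompt concerns days and says nothing about hours. If 10–20% of women trigger it (an assumption), a 10% gain among them moves the arm mean by 600 × 0.10 = 60 to 600 × 0.20 = 120 steps/day, 3–6% of the target. The 6,000 is one illustrative participant. The roughly 600 steps/day quoted in Section 1.2 for men using wearables is a step difference, not a measure of wear.

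**Conclusion.** The asymmetry is real on the text: after baseline, only the feedback arm is described as being prompted to wear and charge the device that measures the primary endpoint. Part of any arm difference in recorded steps, or in evaluability at weeks 4, 8 and 12, could therefore reflect tracker use. Its size and net direction cannot be derived; both turn on an unknown trigger rate, an unknown response and an unstated rule for unworn days.

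A reader might go further and conclude that a difference could not be attributed to walking at all, or that false positives would be heavily inflated. For example, if every control had one more unworn day than every feedback woman, scored as zero at 6,000 steps/day, the shift would be 6000/7 = 857 steps/day. The chance of a significant result with no true effect, at 18 per arm and SD 1,800, would then be about 27% instead of 5%. Nothing supports so uniform a gap from a conditional, fading prompt, and that harm comes from the missing scoring rule as much as from the prompt. This is a cheap improvement, not a flaw that invalidates the comparison.

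**What to change.** In Section 5.1, add one fixed sentence to every email reminder already sent to all subjects, asking them to wear the tracker daily, keep it charged and sync it. Use the same schedule in both arms and no individual trigger. A per-woman trigger for controls would need weekly staff review and linkage, because CHART holds study IDs and no email contacts (Section 5.3.4).

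In Section 8.3, commit to reporting valid days by arm at baseline and at weeks 4, 8 and 12 alongside the primary result, with the definition of a valid day stated. The Appendix 1 counts of monitored and synced days could serve for this table.

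The cost is one sentence in existing emails and one descriptive table from data already collected. Controls get slightly more prompting, which may shrink the contrast a little. Goal feedback may still encourage wear in one arm, so the imbalance is reduced and not removed, and the table is needed to show what remains. Amendment 3 refers to participants who did not complete, so accrual was already under way. The email change may reach only later women, but the table can cover everyone.

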NotmeetSTEP	0 to 6	This value is carried forward from previous intweek If (STEPperday/goalSTEP) >= 0.90 then NOTmeetSTEP = 0 If (STEPperday/goalSTEP) < 0.90 then NOTmeetSTEP = NOTmeetstep+1	Number of consecutive weeks not meeting step goal.
NEWgoalSTEP	5000 to 12000	see "New Goal" section	New step goal

FEEDBACK for WEEKLY Report

SECTION: No title: bar graphs showing progress

VARIABLES:
used to control and provide Feedback

- INTweek
- nDayMonitor
- STEPperDAY
- goalSTEP

FEEDBACK and CONTROLS: INTweek

- 1-6

nDayMonitor

- 0-2
- 3+

FOR STEPS (per day):

Figure:

See PDF from [name]

Criteria 1	FEEDBACK
nDayMonitor	
IF nDaymonitor < 3	Your Week [intweek] goal was [goalstep] steps each day. You did not sync or wear your Fitbit enough last week to give you good feedback.
IF nDaymonitor >= 3	Your Week [intweek] goal was [goalstep] steps each day. You took about [stepPERday] steps each day.

SECTION: My NEW Goals (feedback)

VARIABLES: intWEEK
used to Control Feedback
nDaymonitor
StepPERday
goalSTEP

FEEDBACK and CONTROLS:

NOTE:

- IF nDaymonitor < 3 then...
 - [Blank bar with only intweek label at bottom]
 - Other weeks and goal line stay same

Criteria 1	Criteria 2	Criteria 3	Criteria 4	Description	FEEDBACK
intWEEK	nDayMonitor	Meeting GOAL (Steps 90%+ of Goal)	NOTmeetSTEP	Description	FEEDBACK
1	IF nDaymonitor < 3			Not enough days monitored	
Make your health a priority after getting your cancer diagnosis. We need to know where you're starting in order to help you reach 10,000 steps each day.
 
You did not wear your fitbit enough, or sync, last week to give you a personal goal and meaningful feedback.
 
Please be sure to wear your Fitbit each day, keep it charged, and sync using the app or your home computer.

1	IF nDaymonitor >= 3	ALL	ALL	Wore monitored	
Let's get on track to take 10,000 steps each day to improve your health! Now that you have finished all your cancer treatment, it is an important time to focus on your health! Start with a small change.
 
You can meet your goal by making every little move count! You will get about 1000 steps by taking a brisk 10-minute walk. Fit in 10 minutes of activity when you can. Walk on your work breaks. Make other small changes to your daily routine like parking farther from the store or your work, or taking the stairs.

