11	IF nDaymonitor >= 3	(STEPperday/goalSTEP) < 0.90	NOTmeetSTEP > 2	Wore monitor NOT meeting goal Stuck	Congratulations on finishing this study! You have made some great progress over the last few weeks that will help make you healthier. Remember, small steps are important. Being active will help you look and feel your best.

SECTION: My NEW Goals: (continued)

VARIABLES:

used to Control Feedback

1. ndaysMonitor
2. StepPERday
3. goalSTEP

Weeks	Feedback
1 – 6	Next Week's Goal: Take [NEWgoalSTEP] steps each day You Can Do it !

Computing new Goal For STEPS [NEWgoalstep]:

Criteria 1	Criteria 2	COMPUTE
[nDayMonitor]	[stepPERday] AND [goalSTEP]	[NEWgoalSTEP]=
IF nDaymonitor < 3		NEWgoalSTEP = goalSTEP
IF nDaymonitor >= 3	IF (STEPperday/goalSTEP) < 0.90	NEWgoalSTEP = goalSTEP
IF nDaymonitor >= 3	IF (STEPperday/goalSTEP) >= 0.90	NEWgoalSTEP = stepperday +500
IF nDaymonitor >= 3	IF stepperday >= 12,000	NEWgoalSTEP = 12,000

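### Appendix 1 stops intWEEK, the graph control and the next-week goal line at week 6, although its message table has 11 weeks and messages are planned through week 12; intWEEK 1 is not tied to a study week

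*Combined protocol and SAP*

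**What the plan says.** Appendix 1 sets a six-week range in three places:

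- In the table of feedback variables, intWEEK is limited to 1 to 6 and described only as "Week of intervention".
- In the bar-graph section, the entry 1-6 stands under "FEEDBACK and CONTROLS: INTweek".
- In the continued goals section, the only row of the weeks table is 1 to 6, and it carries the next-week goal line, "Goal: Take [NEWgoalSTEP] steps each day".

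Other parts of the plan assume a longer course. The message table in the same appendix has rows for intWEEK 1 through 11, and all four versions of row 11 congratulate the participant on completing the study. Footnote 1 of Section 6.1 places the feedback arm's messages in study weeks 2 to 12. Section 5.2 promises a weekly message over the three-month period.

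On timing, Section 6.1 labels study week 1 as baseline, and Section 8.3 takes the primary endpoint from the mean steps of week 12, the last week of participation. The appendix captions its worked example "Daily data for 1 participant over first 2 weeks of intervention" but does not say which study week that example starts in.

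**The concern.** Controls receive the tracker without feedback messages (Section 8.1), so Appendix 1 defines the contrast that the trial tests. A programmer or a team repeating the study cannot tell from it whether reports and goals run for 6 weeks or 11. If the shorter range was used, the feedback arm received less than Sections 5.2 and 6.1 describe, and the shortfall came in the weeks before the endpoint.

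Those weeks matter. Section 1.2 reports that in an earlier CHART program for childcare providers, activity rose mid-study and returned to its first-week level as the program ended. That does not show that missing goals cause a decline, but it makes the late weeks a poor place for an unclear rule. Section 5.4 rules out staff contact in weeks 2-12, Section 5.1 adds only reminder emails to sync and log in, and no other route for giving a goal is described.

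The undefined start of intWEEK raises a second question: whether participants in one arm are told that they have finished before the endpoint week has been measured.

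**Working it through.** **1. The plan's own example.** Days above 2,000 steps are averaged, and the new goal is that average plus 500 if the average is at least 90% of the current goal.

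- Week 1: (6,000 + 6,000 + 8,000 + 4,000)/4 = 6,000; 6,000/5,000 = 1.20; new goal 6,500.
- Week 2: (5,000 + 7,000 + 8,000 + 9,000 + 4,000 + 6,000)/6 = 6,500; 6,500/6,500 = 1.00; new goal 7,000.

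Both match the appendix. The goal formula itself has no week limit.

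**2. Counting weeks.**

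- Section 6.1, study weeks 2 to 12: 12 − 2 + 1 = 11 messages.
- Message table: 11 weeks.
- The three limited entries: 6 weeks.
- Reports outside the limit: 11 − 6 = 5 (reports 7 to 11), or 5/11 = 45%.

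The 11-week table and the schedule agree in number; only the 1-6 entries conflict.

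**3. What each limit does if obeyed.** Obeying the limit on intWEEK means that rows 7 to 11 never apply and tailored reports end after the sixth. Obeying only the goal-line row means that reports continue but show no new goal from report 7 on. Report 6 gives the goal for intWEEK 7, so row 7 judges a goal already shown. Rows 8 to 11 judge a goal that was not shown in advance if it has since changed. Whether the backward-looking line ("Your Week [intweek] goal was [goalstep] steps each day. You took about [stepPERday] steps each day") continues depends on what 1-6 governs in the graph section, which is not stated.

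**4. Which study week is intWEEK 1?** A report opens in the week after its data: for the week starting 7 March, the "data below would be used to create report opened to participant on Monday MAR 14th".

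| | intWEEK 1 = study week 1 | intWEEK 1 = study week 2 |
|---|---|---|
| Report k opens in study week | k + 1 | k + 2 |
| Reports 1-11 open in weeks | 2-12 | 3-13 |
| Agrees with Section 6.1 | yes | no |
| Study weeks through 12 whose goal is not displayed (goal row obeyed) | 8-12 (5 weeks) | 9-12 (4 weeks) |
| Row-11 closing text opens in week | 12 | 13 |

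Three features favor study week 1. The reports then fall in weeks 2 to 12. Row 1, when the tracker was worn, does not branch on goal achievement, as suits a baseline week. The under-worn version of row 1 refers to where the participant is "starting in order to help you reach 10,000 steps each day".

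Against it, intWEEK is called a week of intervention while study week 1 is baseline, and the example scores intWEEK 1 against a goal of 5,000. But 5,000 is the floor of the permitted goal range, so it may be a default. The goal-met version of row 11 speaks of the current week, but it looks back under either mapping.

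**The case against.** The strongest reply is that the 1-6 entries are remnants and nobody would apply them. Much supports this. The texts for weeks 6 to 10 repeat those for weeks 3, 4, 5, 4 and 5, as if a shorter program had been extended. The goal-line section's list of controlling variables omits the week, and the under-worn texts in rows 7 to 10 still speak of a personal goal. The limits also cannot all produce the same fault: if intWEEK stops at 6, rows 8 to 11 never judge an undisplayed goal. The graph is in a separate file, and the live configuration is not described.

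This makes a leftover the likely explanation, but does not make the text right. Each way of obeying a limit cuts short something that Sections 5.2 and 6.1 promise, and nothing says which entry governs.

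Other parts of the reply stand and bound the point:

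- None of the goal-not-met texts in rows 8 to 11 mentions a goal. Only the four goal-met texts state a judgement, and it is praise.
- After a missed or under-worn week the goal stays as last shown, so the displayed and computed goals differ only once a week from intWEEK 7 on has been met.
- If report 11 is purely a closing message it needs no next goal, and four reports (7 to 10) lack one rather than five.
- The cap of 6 on the "Number of consecutive weeks not meeting step goal" changes no message, because selection uses only up to 2 versus more than 2.

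A reader might infer that the feedback arm in fact lost its goals, that the comparison is biased toward no difference, or that the closing text lowers week-12 steps. The documents support none of these. Delivery is unknown, messages are seen only on log-in (Section 5.3.4), and all four closing texts promote activity.

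**Conclusion.** The intervention specification contradicts itself and should be corrected. Its extent is 5 of 11 reports outside the stated range, in the weeks leading to the week-12 endpoint, and the feedback arm is weakened only if CHART was set up from those entries. Neither the direction nor the size of any change in steps can be derived, and it may be small. The sample size, alpha and stated power are untouched.

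The study week of intWEEK 1 is not stated. Study week 1 is the better-supported reading but is an inference. Given that reading, the closing text opens at about the start of the endpoint week, in the feedback arm only; under the other mapping it opens after that week and the timing concern falls away. Confidence is medium, because the live configuration and the graph file are not available.

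**What to change.** - Change the three 1-6 entries to 1-11.
- Show the goal line in every report that precedes a study week through week 12. With intWEEK 1 as study week 1, that is all 11 reports.
- State that intWEEK 1 is study week 1, or name the week if it is another. If it is study week 2, Section 6.1 must also change, since reports would open in weeks 3 to 13.
- Use an ordinary goal-based message in any report that opens before the week-12 step window closes, and release the closing text afterwards.
- Check the live CHART configuration against the corrected appendix. If messages have already gone out, report which version was delivered.

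The cost is appendix wording and a configuration check. No new data, visits or participants are needed.
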